## **Ib. Objectives/Purpose of the study**

Our objective is to conduct a prospective randomized trial to assess the utility of using real-time ultrasound imaging in the reduction of forearm fractures in the PED. We also plan to assess provider satisfaction with using ultrasound for the reduction procedure compared to fracture reduction without use of ultrasound. We hypothesize that the use of ultrasound will improve patient outcomes and provider satisfaction. Thus, the primary outcome of the study will be:

- 1) To compare the number of patients requiring a repeat reduction procedure between the experimental group (ultrasound guided fracture reduction) and control group (standard of care forearm fracture reduction).

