### **Secondary Outcomes:**

- 1) To compare provider satisfaction with the reduction procedure between the two groups. Specifically, we will ask providers to determine:
  - I. Providers from experimental group:
    - a. Ease of fracture reduction - scale 1-5, (1=easy 5=very difficult)

---

Ang et al, Ultrasound-guided reduction of distal radius fractures, Am J of Emerg Med, 2010; 28, 1002-1008

Chinnock et al, Ultrasound-guided reduction of distal radius fractures, J of Emerg Med, 2011, 40 (3) 308-312

 Brahm J et al, A Randomized controlled trial of emergency department ultrasound-guided reduction of distal radius fractures, Annals of Emerg Med-Abstracts, 2011 Oct; 58(4), 230

IRB #:

Version 1.2

- b. Ease of using ultrasonography on a 5 point scale (1=easy, 5=very difficult).
- c. Was ultrasound helpful in completing the fracture reduction? a) yes b) no c) uncertain

II. Providers from control group:

- a. Ease of fracture reduction - scale 1-5, (1=easy 5=Most difficult)
- b. Do you think real-time imaging would have been helpful for this reduction?

|

- 2) To compare the adequacy of reduction between groups by measuring and comparing the degree of angulation and displacement on the post reduction x-rays. An orthopedic surgeon who is blinded to the patient's group assignment will read the x-rays. The acceptable degree of angulation will be the same in both groups. The acceptable degree of angulation based on age is less than 20 degrees' angulation for patients younger than 10 years of age and less than 10 degrees' angulation for patients older than 10 years of age.
- 3) To compare the time for the fracture reduction procedure between the experimental and control group.
- 4) To compare the number of patients requiring operative repair after reduction between the experimental and control group.
- 5) To compare the post-reduction ultrasound and x-ray interpretation, including measurement of degree of angulation and displacement on the ultrasound and x-ray for each patient.

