#### **IIId. Number of Subjects**

From a retrospective chart review sampling of displaced forearm fractures requiring reduction from June 1 to August 31, 2015 at CHAM, there were 20 displaced forearm fractures that underwent a closed reduction procedure in the Pediatric Emergency Department. 5 of the 20 displaced forearm fractures (25%) were inadequately reduced and required repeat reduction and/or operative management. Based on a recent study by Wellsh et al, only 6% of patients required repeat fracture reduction when US guidance was used.

In order to observe such a difference with 80% power, the sample size calculation would require a minimum of 56 patients in each group (standard of care vs US-guided reduction) with alpha set at P= 0.05.

Statistical significance will be assessed using mean, percentages, frequency distributions, and p-value. The significance will be set at 0.05. The test statistic used will be the Chi-square test. Confidence intervals will also be obtained. After the primary analysis of the group differences, logistic or normal regression will be used to determine factors related to these outcomes. The significance will be set at 0.05. The statistical approaches will be further developed with the assistance of the statistician in the orthopaedic surgery department following data collection and study approval.

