### **IIIb. Data Collection / Monitoring**

The primary endpoint of the study is comparing the percentage of patients with an adequate degree of angulation on post-reduction x-rays between the experimental group and the control group. X-rays will be performed based on the PED routine standard of care.

Demographic data recorded by the study trained physician will include the patient's name, age, medical record number, date of birth, date of visit, and ultrasound experience of the study-trained physician performing the ultrasound. *The patient identifiers are necessary for patient tracking to match ultrasound findings with X-ray final readings and for clinical follow up.* Type of sedation used, length of procedure and any ultrasound data will be collected and recorded by study trained physicians. Radiographic readings will be collected by the investigators.

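### Further development of the statistical approach is deferred until after data collection, and nothing requires the plan to be final before outcomes are seen by arm

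*Combined protocol and SAP*

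**What the plan says.** Section IIId (Number of Subjects) names a chi-square test, a significance level of 0.05 and confidence intervals. It adds a logistic or normal regression, to follow the primary group comparison and look for factors related to the outcomes. It then states: "The statistical approaches will be further developed with the assistance of the statistician in the orthopaedic surgery department following data collection and study approval".

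The endpoint to which the chi-square test applies is stated in more than one way:

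- Section Ib gives the primary outcome as "To compare the number of patients requiring a repeat reduction procedure between the experimental group" and the control group.
- Section IIIb says "The primary endpoint of the study is comparing the percentage of patients with an adequate degree of angulation on post-reduction x-rays".
- The Secondary Outcomes list places the same radiographic construct second: "To compare the adequacy of reduction between groups by measuring and comparing the degree of angulation and displacement on the post reduction x-rays".
- The control rate behind the sample size is a composite, patients who "were inadequately reduced and required repeat reduction and/or operative management" (5 of 20). The ultrasound rate is for repeat reduction alone: "only 6% of patients required repeat fracture reduction when US guidance was used".

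Sections IIc and IVb say that a patient who has discomfort from, or cannot tolerate, the ultrasound leaves the study. Neither says how that patient is analysed.

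On blinding, Section Ic and the Secondary Outcomes list blind the orthopedic surgeon who reads the x-rays. No other role is described as blinded. The residents who perform the reduction know the arm and record procedure data (IIIa, IIIb), and the investigators manage the data (IIIc).

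**The concern.** The closing sentence of Section IIId is a stated rule about timing, so this is more than an omission. It puts part of the statistical work after the data are in, and no other section sets a lock point or keeps the analyst from the allocation until choices are made.

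A nominal 5% error rate holds when the endpoint, analysis set and test are fixed without knowledge of the results. If they can be fixed afterwards, a reader of the final report cannot tell a planned analysis from one chosen because it looked favourable. What is at stake is the credibility of the primary p-value and of the secondary comparisons.

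**Working it through.** **1. The plan's own figure.** Inputs from Section IIId: p1 = 0.25, p2 = 0.06, power 80%, alpha 0.05. Sidedness is not stated; two-sided is taken here. The mean rate is (0.25 + 0.06)/2 = 0.155 and the difference is 0.19.

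n per group = [1.960·√(2·0.155·0.845) + 0.842·√(0.25·0.75 + 0.06·0.94)]² / 0.19²
= (1.0031 + 0.4156)² / 0.0361 = 2.0129 / 0.0361 = 55.8, so 56.

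This matches the stated 56 per group. With a continuity correction the same formula gives 66. The sample size is therefore not in error, and it corresponds to the uncorrected chi-square.

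**2. What is fixed and what is open.**

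| Item | Status in the document |
|---|---|
| Level, test family, confidence intervals, order of analyses | Stated (IIId) |
| Primary endpoint | Two versions (Ib, IIIb) |
| Patients taken out for ultrasound discomfort | Analysis not stated (IIc, IVb) |
| Continuity correction | Not stated; 56 per group implies none |
| Tests for procedure time, degrees of angulation, 1–5 ease scores | Not stated; a chi-square test does not suit them as recorded |
| Regression type, covariates, outcomes | Not stated; secondary, after the primary comparison |

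The discomfort rule can in practice remove patients from the ultrasound arm only, apart from any control patient scanned at a repeat reduction. Whether they are counted can therefore shift the comparison between arms.

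**3. Size of the endpoint freedom, as illustration.** Suppose both primary endpoints are null, each is tested two-sided at 0.05, and either may be reported as primary. With the two statistics bivariate normal with correlation r, the error is 1 − P(|Z1| < 1.96 and |Z2| < 1.96):

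| Assumed r | Error |
|---|---|
| 0 | 1 − 0.95² = 9.75% |
| 0.5 | 9.1% |
| 0.7 | 8.3% |
| 0.9 | 7.0% |
| 1 | 5.0% |

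The documents give no correlation. A simulation of two binary endpoints, 56 per arm with both null rates assumed at 25%, gave 9.6%, 8.9% and 8.4% at latent correlations of 0.5, 0.8 and 0.9. A latent correlation is on a different scale from r, so the two sets are not directly comparable.

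**4. The continuity correction.** Exact enumeration of all tables at 56 per arm:

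| | Uncorrected | Yates |
|---|---|---|
| Power, 25% vs 6% | 82.7% | 74.4% |
| Size, both arms 25% | 5.1% | 3.0% |
| Size, both arms 15.5% | 5.0% | 2.6% |

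The Yates statistic never exceeds the uncorrected one. No table is rejected by Yates and not by the uncorrected test, so freedom to use either has the same size as the uncorrected test alone.

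**The case against.** The strongest reply is that the sentence says the approaches will be developed *further*. Test, level, intervals, sample-size basis and order of analysis are already written down, and the sentence does not say that endpoints will be chosen later. This stands, and it limits the point to what is still open.

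Second, the 7–9% belongs to the conflict between Sections Ib and IIIb. This also stands. Once one primary endpoint is fixed, that inflation goes, and no figure is available for the rest. The deferral matters here because it lets the conflict be settled late. The analysis set and the secondary tests would remain open even after that repair.

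Third, Section IIIa has repeat reduction decided from displacement on the post-reduction x-ray, and adequate angulation is also judged on post-reduction x-rays. The two endpoints are probably strongly related, so the lower end of the range is the more plausible.

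Three stronger readings are tempting, and the documents do not support them:

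- *That open test and covariate choices add further to the primary error.* The continuity correction adds none (step 4), and the regression comes after the primary comparison.
- *That everyone is unblinded and the choices will be made on results.* The x-ray reader is blinded, and the documents do not say whether the statistician would see arm labels.
- *That someone intends to select a favourable analysis.* Nothing suggests this. The point is only that nothing prevents it.

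**Conclusion.** The point holds in limited form. Section IIId defers part of the statistical work until after data collection, and no section requires the plan to be final before outcomes are seen by arm. The primary endpoint, the handling of patients taken out for discomfort, the secondary-outcome tests and the regression specification could all be settled with results in view.

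The only quantified effect on type I error is 5% rising to about 7–9%. It rests on assumed correlations of 0.9 to 0.5 and on a completely free choice between the two endpoints, and should be read as an illustration. The test version is a question of power, 82.7% against 74.4% at the planned rates, and the stated sample size already points to the uncorrected test. This should be changed before the trial starts. It does not alter the sample size.

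**What to change.** Replace the closing sentence of Section IIId with: *The statistical analysis plan will be completed with the departmental statistician and signed and dated before the first patient is randomised, or at latest before any outcome is tabulated by arm.*

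That plan should:

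- name one primary endpoint, and make Sections Ib, IIIb and IIId agree with it;
- analyse patients as randomised, and say how those taken out for ultrasound discomfort are counted;
- specify the uncorrected chi-square test used for the sample size, with a 95% confidence interval for the risk difference (other tests are defensible, but this one matches the 56 per group);
- name a test for each secondary outcome, including time, angulation and ease scores;
- state the type, outcome and covariates of the regression, labelled secondary.

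Later changes are dated and labelled post hoc.

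The cost is small: the same statistician's work is done earlier, a short signed document is added, and there is less flexibility afterwards. Trial procedures and the number of patients do not change.

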### **III. METHODS AND PROCEDURES**

#### **IIIa. Methods and Procedures**

This will be a prospective randomized, controlled, single blinded study that will take place at the Children's Hospital at Montefiore (CHAM) in the Pediatric Emergency Department (PED). Patients who present to the PED, are confirmed to have a forearm fracture requiring closed reduction in the PED and meet the inclusion/exclusion criteria will be eligible for the study. The decision to perform a closed reduction procedure in the PED will be made by the consulting orthopedic surgeon who will perform the procedure. All eligible patients' pain will be reassessed and managed as necessary as per standard of care. The eligible patient or parent/guardian will be approached by the treating physician or consulting orthopedic resident for written consent. Written assent will be obtained from minors older than 7 years of age (see below for consent timeline/process). After enrollment into the study, patients will be randomized to either the experimental group (ultrasound guided fracture reduction) or control group (standard of care forearm fracture reduction without real-time imaging). Allocation of patients to intervention and control arms will be accomplished by a computer-generated permuted block randomization scheme. An individual in the Department of Orthopaedic Surgery, who is not part of the study team will perform block randomization and will provide the study team with sealed envelopes for treatment prior to the enrollment of any patients in the study. These envelopes will be part of the study package, which include study questionnaires. We will choose blocks of 20 patients in order to reduce or eliminate experimental error contributed by inexperience using the US-guidance at the beginning of the study.

IRB #:

Version 1.2

Consulting orthopedic residents will be trained to perform musculoskeletal sonography for this study (see below for standardized training of study physicians in ultrasound) and will be considered study-trained physicians. All patients will undergo procedural sedation and/or pain management for closed reduction as per standard of care in the PED. The medication used for sedation and/or pain will be determined by the treating PEM physician. Study patients that are randomized to the ultrasound guided group will undergo a point-of-care ultrasound, performed by a study trained physician using a Sonosite Edge ultrasound machine with an L38 linear 10-5 MHz transducer probe.

Prior to the reduction procedure in patients randomized to the experimental group, ultrasound images of the fracture site will be obtained and the maximum degree of displacement will be measured. The ultrasound technique involves placing ultrasound gel over the fracture site and then placing the ultrasound probe in contact with the gel but not with the underlying skin. Both longitudinal and transverse views of the injured area will be obtained. Fractures are identified as an irregularity or interruption of the cortex of the bone. The degree of displacement is measured by drawing two intersecting lines along the edge of the cortex at the fracture site, generating an angle. Displacement measurements are then made by calculating the distance from the normal cortex to the fractured edge of the cortex.

The trained physician will then perform real-time ultrasound imaging as needed during the closed reduction procedure. Real-time ultrasound imaging includes both longitudinal and transverse views of the fracture site, repeated as often as necessary until the best alignment can be obtained. Once the orthopedic resident determines that he/she has obtained optimal alignment and prior to casting, a post-reduction ultrasound image will be obtained and the angle of displacement will again be measured. All ultrasounds performed prior to and after the reduction will be recorded, and the images obtained will include video clips of the ultrasound as well as a saved still picture of the best image of the suspected fracture site. The study-trained physician who performed the ultrasound will then record his/her findings on the data collection form immediately after the procedure and prior to reviewing plain radiographs.

While it has been our experience that the majority of reduction procedures performed in the PED are done without the use of any real time imaging, some orthopedic surgery residents employ the use of the c-arm (fluoroscopy) and/or a portable x-ray machine during the reduction procedure. At his/her discretion, the orthopedic resident may use either of these modalities in both the ultrasound and control group as per standard of care in the PED. The use of these modalities will be recorded.

After the reduction procedure in the ultrasound group and prior to reviewing the post reduction x-ray, the orthopedic resident will complete a brief questionnaire with the following questions.

For the experimental group:

- a. Rate the ease of fracture reduction from 1-5, (1=easy 5=Very difficult)
- b. Was ultrasound helpful in completing the fracture reduction? a) yes b) no c) uncertain
- c. Rate the ease of using ultrasonography on a 5 point scale (1- easy, 5=very difficult).

The control group will undergo fracture reduction without ultrasound guidance as per the current standard of care in the PED. After the reduction procedure in the control group, the orthopedic resident will complete a brief questionnaire with the following questions:

For the control group:

IRB #:

Version 1.2

- a. Rate the ease of fracture reduction from 1-5, (1=easy 5=very difficult)
- b. Do you think real-time imaging would have been helpful for this reduction?

After the reduction and casting is completed, patients in both groups will undergo a post-reduction x-ray. Based on the degree of displacement on the x-ray, the orthopedic surgeon will determine whether the patient needs a repeat reduction, as per routine standard of care. If a repeat reduction is required, the treating physician can choose to use ultrasound at his/her discretion. The angle of displacement will be measured on the post-reduction x-ray by an orthopedic surgeon. Additionally, the angle of displacement measured on the post-reduction ultrasound will be measured and compared to the angle of displacement on the post-reduction x-ray. An expert sonographer will review cases where the ultrasound and x-ray results do not correlate.

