#### | **Ic. Study Design**

The study will be a prospective randomized, controlled, single blinded study. The study is single blinded in that the orthopedic surgeon reading the x-rays and determining the degree of angulation and displacement will be blinded to all patient characteristics and the patient's group assignment.

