### **IVb. Protection against risk**

In the unlikely event that a patient is unable to tolerate the ultrasound procedure, the ultrasound will be discontinued immediately and the patient will be removed from the study. There are no infectious risks from the use of ultrasound in this study; open fractures are excluded, and the US machine will be cleaned per routine procedure after each use.

The risk of patient confidentiality being violated in this study is minimal due to the numerous safeguards that have been implemented (see section IVa).

---

 Simanovsky et al. Sonographic detection of radiographically occult fractures in paediatric ankle injuries. Pediatr Radiol 2005; 35(11):1062-5.

IRB #:

Version 1.2

**V. INVESTIGATOR QUALIFICATIONS AND EXPERIENCE** – see attached CV**VI. SUBJECT IDENTIFICATION, RECRUITMENT AND CONSENT/ASSENT****VIa. Consent and Procedure Timeline / Process**

The PEM attending, fellow or orthopedic resident caring for the patient will determine if the patient is eligible for inclusion in this study. If the patient is eligible and does not meet any of the exclusion criteria, the patient will be asked to participate (see written consent and child assent documents). The patient will be randomized to one arm of the study only after obtaining written consent from the patient  $\geq$  18 years of age or the parent/guardian of a minor and assent if the child is  $\geq$  7 years.

The experimental group will have an ultrasound performed prior to, during and after forearm fracture reduction. The ultrasound procedure involves placing ultrasound gel over the fracture site. The ultrasound probe is then placed in contact with the gel but not with the underlying skin. Images of the bony cortex are obtained in both longitudinal and transverse orientations and recorded on the ultrasound hard drive. After completion of the post-reduction ultrasound, the ultrasound gel will be removed, and the patient will undergo routine casting/splinting and post-reduction x-ray as per the Pediatric ED standard of care. The control group will undergo the standard of care fracture reduction with post-procedure x-ray images.

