**VIb. Subject Identification/Recruitment/Consent**

Potential subjects will be recruited by PEM attendings, PEM fellows and orthopedic residents who have participated in the formal ultrasound fracture diagnosis training session. Subjects will be recruited solely on the basis of inclusion and exclusion criteria. The consent/assent will be obtained and then documented by the study trained physician who is performing the ultrasound.

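### One fixed, disclosed block size of 20 in an unblinded single-site trial lets anyone who tallies past assignments know the end of each block; large, hidden, varying blocks would be a cheap improvement

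*Combined protocol and SAP*

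**What the plan says.** Section IIIa gives the method: "Allocation of patients to intervention and control arms will be accomplished by a computer-generated permuted block randomization scheme". It names one block size and a reason for it: "We will choose blocks of 20 patients in order to reduce or eliminate experimental error contributed by inexperience using the US-guidance". The trial runs in one emergency department, and neither stratification nor variation in block size is described.

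Concealment rests on envelopes. An individual outside the study team makes the list and "will provide the study team with sealed envelopes for treatment prior to the enrollment of any patients in the study". Section IIIa adds: "These envelopes will be part of the study package, which include study questionnaires". Numbering, opacity and order of use are not stated. Section VIa puts allocation after consent: "The patient will be randomized to one arm of the study only after obtaining written consent".

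On blinding, section Ic says: "The study is single blinded in that the orthopedic surgeon reading the x-rays". Nobody else is described as blinded. On entry, section VIb says: "Potential subjects will be recruited by PEM attendings, PEM fellows and orthopedic residents who have participated in the formal ultrasound fracture diagnosis training session". The same section has consent taken by the physician who performs the ultrasound. Section IIIa adds: "The decision to perform a closed reduction procedure in the PED will be made by the consulting orthopedic surgeon who will perform the procedure".

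**The concern.** A sealed envelope hides the next card. It does not hide what can be worked out from earlier assignments when the block size is known. Once one arm has used its 10 places in a block of 20, every remaining assignment in that block is determined. The size stands in a protocol that the enrolling physicians can be expected to know, and those physicians learn the arm of each patient they treat.

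They also have discretion before randomisation: whether a fracture is reduced in the department, and whether the family is approached. Section Ib states the hypothesis that ultrasound improves outcomes. A recruiter who knew the next arm could, even without intent, approach or pass over a family according to how difficult the fracture looked. Such selection acts before randomisation, so neither blinded x-ray reading nor the chi-square test can undo it.

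The stated reason for blocks of 20, early inexperience with ultrasound, is a reason to balance the arms over time. It does not require a constant or published block size.

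**Working it through.** **Inputs.** Block size 20 and a single site (section IIIa). Failure rates of 25% (control) and 6% (ultrasound), 56 per group, 80% power and alpha 0.05 (section headed Number of Subjects). Two inputs are assumptions: 1:1 allocation within blocks, inferred from the equal group sizes, and envelopes opened in list order, which is not stated.

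**The plan's own figure.** With a pooled rate of 0.155, two-sided alpha 0.05 and no continuity correction:

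n = [1.96·√(2·0.155·0.845) + 0.8416·√(0.25·0.75 + 0.06·0.94)]² / 0.19² = 2.013 / 0.0361 = 55.8, so 56 per group. The stated size reproduces, with power 80.2%.

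**Assignments known for certain.** In a block with m = 10 per arm, the last k assignments all go to one arm with probability 2·C(20−k, 10)/C(20, 10), where C(20, 10) = 184,756.

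| Last k places known | Share of blocks |
|---|---|
| 1 | 100% |
| 2 | 2·43,758/184,756 = 47.4% |
| 3 | 2·19,448/184,756 = 21.1% |
| 4 | 2·8,008/184,756 = 8.7% |

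The mean number known is 2m/(m+1) = 20/11 = 1.82 per block, or 9.1%. The planned 112 patients make 5 full blocks plus 12 of a sixth, giving 5 × 1.82 ≈ 9.1 certain assignments, or 8.1% of 112. Simulation also gives 9.1.

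**Guessing from the running imbalance.** Always naming the arm with more places left gives an expected 10 + 2¹⁹/184,756 − 0.5 = 12.34 correct of 20, or 61.7% per full block. Over 112 patients it is about 61%.

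**Effect if recruiters act only on certain assignments.** Assume no true effect and a 25% failure rate. When the next arm is certain, suppose enrolled patients' risk is lowered by δ if it is ultrasound and raised by δ if it is control. The documents give no value for δ, so a range of 5 to 15 points is shown. The false difference is 2 × δ × 0.081:

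- δ = 5 points: 0.8 points
- δ = 10 points: 1.6 points
- δ = 15 points: 2.4 points

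In simulation (20,000 runs per setting, chi-square without correction), one-sided rejection favouring ultrasound goes from about 2.5% with no shift to about 3%, 4% and 5%.

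**Effect if recruiters act on every imbalance.** At 61% correct, the net excess of right over wrong guesses is 0.61 − 0.39 = 0.22. The false difference is 2 × δ × 0.22, or 2.2 to 6.6 points.

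**After the change.** With hidden sizes drawn from 16, 20, 24 and 28, simulation found no certain assignments in 4,000 runs, with 60.7% of guesses correct. Small varying blocks raise correct guesses to 68.0% (sizes 4/6/8) or 66.3% (6/8/10). A small fixed block of 4 would leave 33.3% of assignments certain.

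**The case against.** The strongest reply is that a block of 20 is already hard to predict and that the documents do not show anyone able to exploit it. Much of this stands. A reader might infer that recruiters see every past assignment. No section says so: a clinician learns the arm of a patient he or she treats, recruitment is spread over attendings, fellows and residents, and no shared log or block-start marker is described. The chart review found 20 cases in about three months, so an exact count would have to be kept over a long period. The direction of steering is also assumed; residents might prefer ultrasound for harder fractures, which would bias against it.

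A reader might also take the larger bias (2.2 to 6.6 points, with false-positive rates of roughly 5-12%) as the harm at issue. That comes from guessing on the running imbalance, which varying the block size leaves at about 61% correct. It cannot be credited to the fix.

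What does not stand is that envelopes and randomisation after consent settle the matter. The deduction uses past arms, not an opened envelope, and nothing in the documents prevents a tally.

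**Conclusion.** The weakness is that the block size is both constant and disclosed, not that it is 20. Under 1:1 blocks, envelopes used in order and a complete pooled tally, about 9 of 112 assignments can be known before the family is approached. Only the last place is certain in every completed block, so it would be too strong to say that several are known each time. Acting on those alone, with an assumed shift of 5 to 15 points, gives a worst-case false difference of 0.8 to 2.4 points against the planned 25 − 6 = 19. The one-sided false-positive rate becomes about 3-5% instead of 2.5%. The documents do not show that concealment has failed or that results would be materially biased. The point is a cheap improvement to a sound scheme, worth making because selection at entry cannot be repaired after enrolment.

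**What to change.** In section IIIa, replace the fixed block size with large permuted blocks of randomly varying size. The individual outside the study team who already prepares the list should choose the sizes, for example between 16 and 28, and hold them until enrolment closes. Remove the sizes from the protocol and from any other document that recruiters hold. Keep the computer-generated list and the sealed envelopes. Do not move to small blocks, which make guessing easier.

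Make the change before the list is generated. The documents do not show whether enrolment has begun; if it has, apply the change to the remaining blocks.

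The cost is a short protocol edit and one new list, with no extra patients, staff or procedures; the sample size stays at 56 per group. The arms may differ by a few patients if enrolment stops mid-block. The present scheme already allows this: at 112 patients the sixth block stops after 12, so the split can reach 60 to 52 (50 + 10 against 50 + 2). Power for 25% versus 6% is still 79.4-80.5% at that split, depending on which arm is larger.
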